#### B.4.9. Existing Challenges & Barriers

To test our study hypothesis in females, it is critical to produce and maintain serum progesterone levels consistent with those observed in the Luteal phase (6-14 ng/mL; Yee et al, 1999). To do this, we considered many different options for the delivery of exogenous hormones. First, we decided not to use combined synthetic progestin-estradiol hormonal contraceptive pills because this option would further complicate the study design by introducing another variable (exogenous estradiol; Goletiani et al 2007). Second, we also considered using synthetic progestin-only hormonal contraceptive pills. However, as we have observed in our current study, they also do not result in levels of serum progesterone consistent with the Luteal phase. Further, synthetic progestin has more risks associated with it than natural progesterone (Goletiani et al 2007). Next, delivery of progesterone via intravaginal or rectal suppository, or intramuscular injection was eliminated because the serum progesterone levels would still be substantially lower than those typical of Luteal phase. Therefore, using natural micronized progesterone (generic Prometrium) is the best way to ensure serum progesterone levels remain consistent with levels observed during the Luteal phase. Since the half-life of natural progesterone is short, twice daily dosing is necessary. While there may be a question of subject compliance with taking two oral doses per day, we will confirm compliance via the assessment of serum progesterone levels at all study visits postpartum. Natural progesterone is also the easiest way to administer supplemental progesterone for male participants and has been successfully done in other studies (Goletiani et al 2007). On a related note, a second challenge is estrogen. Estrogen fluctuates naturally during the menstrual cycle (Yee et al 1999), and has also been shown to be associated with the facilitation of drug abuse behaviors (Carroll & Anker, 2010). While it is impossible to remove estrogen from our sample population, we will measure it (via blood samples to measure serum estradiol levels) and consider it in our analyses.

**Table 2. Timeline of Study Events**

#### B.4.10. Timeline

The study timeline is displayed in Table 2.

#### B.4.11. Future Directions

	Year 1				Year 2				Year 3				Year 4				Year 5			
	1	2	3	4	1	2	3	4	1	2	3	4	1	2	3	4	1	2	3	4
Training Staff and Study Preparation	X	X																		
Subject Recruitment		X	X	X	X	X	X	X	X	X	X	X	X	X	X	X				
Subject Follow-up			X	X	X	X	X	X	X	X	X	X	X	X	X	X	X	X	X	X
Data Entry and Cleaning				X	X	X	X	X	X	X	X	X	X	X	X	X	X	X	X	X
Analysis and Report Writing																	X	X	X	X

The expected outcomes of this project will be a better understanding of the relationship between sex, sex hormones, impulsivity and smoking behavior. Upon completing this project, we intend to continue our exploration into the role of sex hormones on smoking behavior. Specifically, if our expectations are confirmed, we plan to conduct a similar study in a time associated with increased risk for smoking relapse for both men and women – the postpartum period.

### **C. Inclusion of Children.**

Children (under 18 years old) are not included since young age is associated with menstrual cycle irregularities (e.g., anovulation). Further, since this study requires the continuous (or a recent history) of regular use of cigarettes, it is unlikely adolescents will meet this criterion. Young men and women (e.g., aged 18-20 years) will be recruited for participation in our study. The trial site is at the University of Minnesota, which has a large undergraduate population. Campus media will be also used to recruit young men and women. We will also target venues and institutions frequented by young non-college men and women (bars, festivals, coffee shops, and community events) to ensure the sociodemographic diversity of the youngest component of our participant sample.

### **D. Inclusion of Women and Minorities**

This study will be recruiting both men and women because the research question addressed is designed to assess sex differences. We are looking specifically at the effects of a female sex hormone (progesterone) on smoking cessation in men and women who are motivated to quit smoking. The study will use participants recruited from the greater metropolitan area of Minneapolis and St. Paul, via mass media advertisements. The Twin Cities metropolitan area has a sufficiently large female smoking population to ensure an adequate sample. We have been successful in recruiting similar numbers of women in similar periods of time in previous studies. Estimates indicate that as of 2009 the Minneapolis and St. Paul, Minnesota Twin Cities metro area included approximately 50.5% female and 20.2% of the population in the racial minority groups (Black= 11.0%, Asian = 5.8%, American Indian = 1.2%, other = 4.0%) and the Hispanic population is 6.4%. If minority women do not respond to the advertisements, we will make special efforts to solicit their participation by advertising in local neighborhood newspapers with high minority readership (such as the Southside Pride, Phillips/Powderhorn, and Riverside Editions); by posting flyers in free clinics in the metro area who service minorities (e.g., Community University Healthcare Center, Pilot City); and by identifying contacts in churches, health centers, and community centers with high minority participation and disseminating information regarding the study opportunity; and once we have garnered initial contact with participants we receive multiples word of mouth referrals. Our current study has been successful in recruiting a diverse sample in that of the 163 participants enrolled to date 49% are White, 33% are Black, 8% are more than one race and 10% are other.

## **Data Safety and Monitoring Plan (DSMP): 1 P50 DA033942-01**

### **PROJECT 1 – Sex Differences and Progesterone:**

### **Association with impulsivity and smoking cessation**

#### **Summary**

This is one of two clinical trials for the SCOR entitled: *Sex Differences and Progesterone Effects on Impulsivity, Smoking, & Cocaine Abuse*. The DSMP is described below. Organization and implementation of the Data Safety and Monitoring Board functions will be administered by the Service Core (B) of the P50 ([name], Director). This will be undertaken in close coordination with the Principal Investigators of the two clinical Projects (Drs. [name] and [name]) and the overall SCOR Director ([name]), co-Director ([name]) and study staff members.

#### **A1. Study Design and Implementation**

This is a 12-week, two arm (progesterone-PRO- versus placebo-PBO), prospective, parallel groups, randomized placebo-controlled trial examining effects of PRO, compared to placebo (PBO), as well as sex differences on impulsivity and smoking cessation outcomes in females and males who are motivated to quit smoking.

#### **Outcome Measures**

The primary focus and outcome measure will be prevalence of smoking relapse at Week 4 using point prevalence definition of abstinence. This will be measured via self-report, carbon monoxide

breathalyzer, and urinary cotinine. Secondary outcome measures include days to relapse (also measured by self-report, carbon monoxide breathalyzer, and urinary cotinine using continuous abstinence and prolonged abstinence definitions) and impulsivity measures (self-report questionnaires including Behavioral Inhibition / Activity Scales, Barratt Impulsiveness Scale, and Brief Self Control Scale; and computer tasks including Delay Discounting, GoStop Task, Balloon Analogue Risk Task, and Immediate/Delayed Memory Task).

[figure not shown]
#### **Setting, Recruitment, Subjects**

Setting: This project will be conducted at the Delaware Clinical Research Unit (DCRU). The DCRU has both inpatient and outpatient resources for the spectrum of biomedical research including special capabilities that were developed for study of substance use disorders. The Clinical and Translational Sciences Institute (CTSI), runs the DCRU and functions parallel and support the activities of the NIH funded CTSA, which predated it. The DCRU includes: reception area, examination rooms, meeting rooms, clinical interview rooms, testing rooms for computer based performance tasks, a wet lab for handling bloods and other specimens, freezers (to -80°C), all essential staff offices, each with multiple telephone and computer lines through the University of Minnesota servers, a locked limited access protocol, equipment and medication rooms, as well as secure cabinets for study files and essential supply and support areas and services.

Recruitment: To meet recruitment goals, we will enroll a total of 250 subjects (~6 subjects/month) to ensure a final sample size of 100 females and 100 males. Our primary recruitment method will be advertising in the mainstream media. While this type of recruitment can be challenging, our team has been successful with this form of recruitment. For example, our current study recruiting females between the ages of 18-40 has had success with Facebook advertising. Specifically, over the past seven months we have advertised on Facebook resulting in 6,483 clicks to our website, an estimated 180 phone calls to our clinic and an enrollment of 29 subjects (~4 subjects/month). We regularly use television, radio, mailings, and other internet sources to identify study subjects with similar success. Using all of these methods, we have successfully enrolled ~8 subjects/month over the past year in our two ongoing tobacco use research studies. Additional advertising and the unique character of this study will further assure an ample sample.

#### **Subjects and Eligibility Criteria**

Two hundred and fifty subjects, 50% female, will be consented to achieve the final sample of 200 subjects (50% female). The inclusion and exclusion criteria are:

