#### B.4.1. Study Design

This double-blind, clinical trial (Figure 4) will prescreen an estimated 600 potential subjects, consent and evaluate approximately 300 potential subjects and ultimately enroll 250 subjects to ensure 200 subjects provide a primary relapse outcome measure at four weeks after quit date. Subjects will be stratified by sex then randomized to one of two groups (n=100 per group / 50% female): Progesterone (PRO) or Placebo (PBO). Telephone screening and visit invitation (20 minutes) leads to the consent process and in-person screening including medical-psychiatric evaluation for inclusion/exclusion (two visits, two hours each), then randomization and medication induction (seven days), stable medication (70 days) with medication reduction and final evaluation for secondary outcomes (over the last seven days). These procedures will be conducted as described below.

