#### B.4.2. Setting, Recruitment, Subjects

Setting: This project will be conducted at the Delaware Clinical Research Unit (DCRU). The DCRU has both inpatient and outpatient resources for the spectrum of biomedical research including special capabilities that were developed for study of substance use disorders. The Clinical and Translational Sciences Institute (CTSI), runs the DCRU and functions parallel and support the activities of the NIH funded CTSA, which it predated.

The DCRU includes: reception area, examination rooms, meeting rooms, clinical interview rooms, testing rooms for computer based performance tasks, a wet lab for handling bloods and other specimens, freezers (to -80°C), all essential staff offices, each with multiple telephone and computer lines through the University of Minnesota servers, a locked limited access protocol, equipment and medication rooms, as well as secure cabinets for study files and essential supply and support areas and services.

**Recruitment:** To meet recruitment goals, we aim to enroll a total of 250 subjects (~6 subjects/month) to ensure a final sample size of 100 females and 100 males. Our primary recruitment method will be advertising in the mainstream media. While this type of recruitment can be challenging, our team has been successful with this form of recruitment. For example, our current study recruiting females between the ages of 18-40 has had success with Facebook advertising. Specifically, over the past seven months we have advertised on Facebook resulting in 6,483 clicks to our website, an estimated 180 phone calls to our clinic and an enrollment of 29 subjects (~4 subjects/month). We regularly use television, radio, mailings, and other internet sources to identify study subjects with similar success. Using all of these methods, we have successfully enrolled ~8 subjects/month over the past year in our two ongoing tobacco use research studies.

**Subjects and Eligibility:** Females 18-50 years of age with regular menstrual cycles and males, 18-60 years of age, (n=300; 50% females) will be enrolled who are current smokers and are motivated to quit smoking.

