## Enrollment Table

Study Title: Progesterone, Impulsivity and Smoking Cessation

Total Planned Enrollment: 250

TARGETED/PLANNED ENROLLMENT: Number of Subjects			
Ethnic Category	Females	Males	Total
Hispanic or Latino	4	4	8
Not Hispanic or Latino	121	121	242
Ethnic Category: Total of All Subjects *	125	125	250
Racial Categories			
American Indian/Alaska Native	4	4	8
Asian	4	4	8
Native Hawaiian or Other Pacific Islander	1	1	2
Black or African American	15	15	30
White	101	101	202
Racial Categories: Total of All Subjects *	125	125	250

\* The "Ethnic Category: Total of All Subjects" must be equal to the "Racial Categories: Total of All Subjects."

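### Consent and enrolment each carry two conflicting numbers, and the monitoring plan's 250 consented cannot yield 200 completers on the protocol's own recruitment figures

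*Combined protocol and SAP*

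**What the plan says.** The recruitment sequence is stated in several places.

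- **Protocol B.4.1, Study Design:** "consent and evaluate approximately 300 potential subjects and ultimately enroll 250 subjects to ensure 200 subjects provide a primary relapse outcome measure". Consent, enrolment and completion are three separate steps, with about 300, 250 and 200 people.
- **Protocol B.4.2, Recruitment:** "we aim to enroll a total of 250 subjects (~6 subjects/month) to ensure a final sample size of 100 females and 100 males".
- **Protocol B.4.2, Subjects and Eligibility (the next paragraph):** "n=300; 50% females) will be enrolled who are current smokers and are motivated to quit smoking".
- **Protocol B.4.7 and the DSMP section Power Analysis and Sample Size:** 125 women and 125 men enrolled, to obtain 100 completers of each sex.
- **DSMP, Setting, Recruitment, Subjects:** "we will enroll a total of 250 subjects (~6 subjects/month) to ensure a final sample size of 100 females and 100 males".
- **DSMP, Subjects and Eligibility Criteria (directly after):** "Two hundred and fifty subjects, 50% female, will be consented to achieve the final sample of 200 subjects (50% female").
- **DSMP, Enrollment Table:** "Total Planned Enrollment: 250".

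Consent is therefore about 300 in one place and 250 in another. Enrolment is 250 in six places and 300 in one.

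**The concern.** Consent and randomisation are different events in this trial, and people are lost between them. Under protocol B.4.3, consent is taken at Screening Visit 1. The medical and psychiatric evaluation follows. Women with no LH surge in two months are then removed as ineligible (estimated at under 5%). Randomisation happens only at the Baseline Visit. The later Rules/Changes list adds a minimum smoking rate at baseline, with those below it filed as screen failures, and liver enzyme limits. Section B.4.1 itself allows for losing about 50 of 300 over this stretch.

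The DSMP sentence leaves no room for that loss. If a reader or an oversight body took 250 as the number to consent, the trial would fall short of the 200 completers that B.4.3 (Study Adherence) names as the goal for powering the primary outcome. Even without a cap, the DSMB is to be shown expected against actual recruitment. That comparison, and the screen-failure count in the participant flow, depend on whether 250 means consented or enrolled.

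**Working it through.** **Inputs**

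- Enrolled per consented: 250/300 = 83.3% (B.4.1).
- Completers per enrolled, as implied by B.4.1: 200/250 = 80%, a loss of 20%.
- Drop-out as stated in B.4.7 and B.4.8: 25% before the primary endpoint.
- Design for each sex (B.4.7): placebo relapse 66%, odds ratio 3.5, two-sided alpha 0.025, Pearson chi-square test, 1:1 allocation, 100 completers (50 per arm).

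**Step 1. Reproduce the plan's power.** The placebo odds are 0.66/0.34 = 1.941. Dividing by 3.5 gives 0.555, so the relapse rate on progesterone is 0.555/1.555 = 0.357. The normal approximation is

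power = Φ{ [ |p1 − p2| − z·√(2·p̄(1 − p̄)/n) ] / √[ (p1(1 − p1) + p2(1 − p2))/n ] }

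with z = 2.241, p1 = 0.66, p2 = 0.357 and p̄ = 0.508. At n = 50 per arm this is Φ[(0.303 − 2.241 × 0.100)/0.0953] = Φ(0.83) = 79.7%. The plan's 80% is reproduced.

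**Step 2. When does 250 consented give 200?** Only if every consented person is enrolled and later loss is 20%: 250 × 1.00 × 0.80 = 200. The first condition conflicts with B.4.1 and the second with the stated 25%.

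**Step 3. Completers if consent stopped at 250.** Enrolled: 250 × 250/300 = 208.

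| Later loss | Completers | Per arm within sex | Power at OR 3.5 |
|---|---|---|---|
| 20% (implied by B.4.1) | 208.3 × 0.80 = 167 | 41.7 | 71.0% |
| 25% (stated) | 208.3 × 0.75 = 156 | 39 | 67.7% |

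**Step 4. Separate the two causes.** With the full 250 enrolled and 25% drop-out, completers are already 250 × 0.75 = 187.5. The 250 target equals 200 × 1.25, whereas allowing for 25% loss needs 200/0.75 = 267. So of the 44 missing in the 25% row (200 − 156), about 12 (200 − 187.5) arise from the drop-out allowance whatever the consent number is. Using B.4.1's own 80% retention removes that component: the part due to the DSMP sentence alone is the drop from 200 to 167.

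**Step 5. Numbers that would be consistent.** At 20% loss: 200/0.80 = 250 enrolled and 250/(250/300) = 300 consented, which is the B.4.1 sequence. At 25% loss: 267 enrolled and 266.7/(250/300) = 320 consented.

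**The case against.** The best reply is that the intended target is not in doubt. An enrolment of 250 appears in B.4.1, B.4.2 (Recruitment), B.4.7, and three places in the DSMP, one of them immediately before the sentence at issue. B.4.8 agrees, at about 125 of each sex. The DSMP most naturally reads as consented written for enrolled, and the stray 300 in B.4.2 matches the consent number in B.4.1. That stands, and it makes this a correction of wording rather than of design.

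A reader might infer that the trial is set to finish with about 156 completers. The documents do not support this. No passage makes 250 consents a stopping point, and no approved consent ceiling is given. B.4.3 sets the goal as 200 completers and replaces people who attend no visit after screening. B.4.8 prepares randomisation tables for up to 150 of each sex. The 156 also includes the separate drop-out problem.

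A reader might also infer that the estimated 600 pre-screened in B.4.1 is contradicted by the yield in B.4.2, where Facebook advertising produced "an estimated 180 phone calls to our clinic and an enrollment of 29 subjects", or 29/180 = 16.1%, against 250/600 = 41.7%. This does not follow. The 16.1% comes from another study, from one advertising channel, in women aged 18-40, with an estimated call count. Half of this trial is men, and a call to the clinic need not be a completed pre-screen. The same section reports about 8 enrolled per month across all methods, against about 6 needed here.

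What remains is that two governing sections give different numbers for consent, and adjacent paragraphs of B.4.2 give different numbers for enrolment.

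**Conclusion.** The inconsistency is real and should be corrected. The DSMP's 250 consented for a final sample of 200 cannot be reached on the protocol's own figures, and n = 300 enrolled in B.4.2 conflicts with every other enrolment statement.

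Its consequence is conditional. If 250 consents acted as a limit, completers would number about 167 on the B.4.1 yields (power about 71%), or about 156 with the stated 25% drop-out (power about 68%), compared with 79.7% for 200 completers. These figures assume that the planned 250/300 screening yield holds, that losses fall evenly across sex and arm, and that the plan's 66% relapse rate and odds ratio of 3.5 are true. All three powers use the normal approximation. An exact calculation must be compared with its own baseline: it gives 78.3% at 50 per arm and 71.3% at 39.

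The likeliest explanation is a slip in wording, so this is a point of consistency and reporting rather than evidence of an underpowered trial.

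**What to change.** 1. In the DSMP, Subjects and Eligibility Criteria, state approximately 300 consented and 250 enrolled and randomised, to obtain 200 completers.
2. In protocol B.4.2, Subjects and Eligibility, change the 300 from enrolled to consented.
3. Use the B.4.1 sequence, with the same terms for each step, wherever these numbers appear.
4. If the enrolment target is revised to allow properly for 25% drop-out, move the consent number with it: about 267 enrolled and 320 consented. Steps 1 to 3 alone make the documents agree, but at 25% drop-out they still give 187.5 completers.

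The pre-screening estimate of 600 needs no change on this evidence.

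Steps 1 to 3 cost a few words and leave the randomisation target as it is. If the consent number on file with the review board is 250, which the documents do not show, one administrative amendment would also be needed.

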### Inclusion Criteria

1. Males between 18 and 60 or females between 18 and 50 years of age;
2. Self-reporting smoking  $\geq 5$  cigarettes/day for at least the past year;
3. Motivated to quit smoking (self-report  $\geq 7$  on 10-point Likert-type scale);
4. Stable physical/mental health;
5. Self report of regular menstrual cycles (female only);
6. Willing to use a double-barrier contraception method if sexually active and not surgically sterilized;
7. English fluency;
8. Understanding the study procedures and able to provide informed consent;
9. Ability to participate fully in research elements for the duration of the trial.

### Exclusion Criteria

- 1) Current use of other types of tobacco, nicotine replacement therapy, or smoking cessation medications;
- 2) Current or recent (< 3 months) breastfeeding (females only),
- 3) Current or planned pregnancy within the next three months (females only);
- 4) DSM-IV diagnoses for, bipolar disorder, ADHD, or major depressive disorder within the last 3 month.
- 5) Substance dependence within the last 3 month with the exception of nicotine dependence and non-daily use of marijuana.
- 6) Use of psychotropic medications;
- 7) Current use of exogenous hormones, finasteroid (propecia), efavirenz, red clover, ketoconazole and other drugs that are CYP3A4 inhibitors
- 8) Conditions contraindicated to progesterone treatment (including, but not limited to, thrombophlebitis, deep vein thrombosis, pulmonary embolus, clotting or bleeding disorders, heart disease, diabetes, history of stroke, allergy to peanuts, hypersensitive to progesterone and liver dysfunction).

### **Screening and Visit Procedures**

The first clinic visit (i.e. Screening Visit 1) will occur within seven days of the onset of menses in females and within two weeks of the telephone interview for males. A brief description of the study will be provided to determine if the subject wishes to proceed with the informed consent process. If agreeable, the informed consent process will be initiated with the candidate subject. Responses will be provided to all candidate subject queries. If the subject agrees to participate, she or he will sign the consent, be provided with a copy of the signed document, and screening will be initiated. Screening will determine final eligibility as determined by meeting inclusion criteria without any exclusionary conditions. Screening will include a general medical examination including history, measurements of height, weight, blood pressure, heart rate, and expired carbon monoxide will be obtained. Female subjects will provide a urine sample that will be used for a pregnancy test. A blood sample will be obtained to assess serum hormone levels and a psychiatric interview will be completed by trained study staff. Subjects will complete forms to measure smoking-related symptomatology, mood, and potential confounders (i.e. age, education, partner smoking, motivation to quit smoking, level of nicotine dependence). At the end of this visit subjects will schedule their next visit and receive compensation for their time.

The second visit (i.e. Screening Visit 2), completed within three days of Screening Visit 1, will include a series of computer tasks to measure impulsivity, followed by training on study procedures and compensation for their time.

A Baseline Visit will occur seven days prior to the subjects assigned quit date. Females will have their assigned quit date set seven to nine days after ovulation. Ovulation will be determined through the use of urine ovulation tests that female subjects will use daily for ten days in a row. Males will have their assigned quit date matched to a female subject for a similar delay and procedure completion. At this visit subjects' weight, blood pressure, heart rate, and carbon monoxide level will be measured. They will also provide urine and blood samples (20cc) for later measurement of nicotine exposure (specifically nicotine and cotinine) and hormone levels (specifically progesterone and estradiol), respectively. At this visit subjects will receive their study medication and be provided regimen/administration instructions. They will also receive brief smoking cessation behavioral counseling, be compensated for their time, and receive a schedule of all follow-up visits.

At the follow-up visits (weekly visits, Week 0 - Week 12) all subjects will have their weight, blood pressure, heart rate and expired carbon monoxide measured. The subjects will provide urine (nicotine, cotinine) at all visits and blood (progesterone, estradiol) samples at visits 0-4, 8 and 12 and complete several forms to measure smoking-related symptomatology, mood, and related items. The study nurse will assess their adverse events. At the end of each visit subjects will receive additional behavioral counseling, additional study medication and be compensated for their time.

Subjects could earn up to \$480 for their study participation (\$25 for screening visit x 2 screening visits + \$20 for baseline visit + \$20 for follow-up clinic visits x 13 visits + \$75 bonus for missing less than three visits + \$75 for completing the study).

